9.2.1 Site Survey

At the time the NCORP site opens the study, the CCDR leader will complete the "Site Survey" which asks analytic numbers for colorectal cancer at their site, resources available at their institution (i.e. social worker, financial counselor, navigator), and institutional practice regarding referrals for financial concerns. Details of where the data for of these variables can be found are included in the form. Each site with an individual CTEP ID is required to fill out one "Site Survey" within 30 days of the first participant enrollment.

9.2.2 Baseline Clinical Form

This form should be completed within 14 days of registration. For participants who choose paper surveys, the date the survey was completed (date signed) must be within 14 days of starting radiation or chemotherapy. It contains questions related to type of malignancy (colon versus rectum) and if chemotherapy is planned. These two variables (malignancy type and chemotherapy use) will be used for stratification. In the case that it is uncertain if chemotherapy is planned, the site research coordinator will choose the option "uncertain", and this question will again be asked in the 3 month follow-up form. This form will also ask about the insurance status of participant. Because we hypothesize that the site will collect more accurate insurance information when compared to patient knowledge of insurance information, when there is a discrepancy, we will use the response from the site in analysis.

9.2.3 Follow-up Clinical Form

This form will be completed by the research coordinator at 3, 6, 12, and 24 month time points. It contains questions regarding vital status (dead/alive), chemotherapy use, performance status, stage, status of

treatment, if there was any insurance changes, and if the participant required help from a caregiver from their knowledge.

9.2.4 24 Month Clinical Form

This form is completed once the participant has completed 24 months of study. This form contains questions on vital status, reasons for being off study, and questions regarding adherence to guidelines.

9.2.4.1 Adherence to guidelines questions

There are questions contained within the "24 Month Assessment" that ask if the patient has received a colonoscopy, sigmoidosocpy, and barium enema since completing therapy (and how many months this test was performed after surgery). These adherence questions also include how often the patient has been examined by their oncologist and had a serum CEA performed. We will define adherent versus non-adherent according to below questions and responses.

Considered ADHERENT if they answer the following (must have ALL) in bold.

Has the patient received a colonoscopy, sigmoidoscopy, or barium enema at some point since their initial surgery (if applicable)?

- Yes
- If yes, how many months since surgery was it completed
- No
- Unsure

How many times has the patient been seen by their oncologist for a history/physical since ending treatment?

- The patient has not been seen by their oncologist since ending treatment
- Once
- Twice
- More than twice
- I don't know the reason

How many times has the patient had a carcinoembryonic (CEA) serum checked since ending treatment?

- The patient has not had a CEA checked since ending treatment
- Once
- Twice
- More than twice
- I don't know

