This study will be conducted through NCORP community sites and minority/underserved sites across the NCI network. Enrollment will be limited to these sites in order to explore the financial experiences of those treated for cancer in the community setting. The infrastructure of resources (i.e. social workers, navigators, financial counselors) may be different at NCORP community sites when compared to large comprehensive cancer centers. Because most patients with these types of common malignancies are treated in the community setting, utilizing NCORP sites will provide a more representative picture of the financial experience of cancer patients in the United States.

Rev. Add1 6.3 Screening, Consent and Patient Registration

Patients from a gastroenterology, surgical oncology, radiation oncology, or medical oncology clinic with newly diagnosed colon or rectal cancer are potential candidates for the study. Participants must enroll within 60 days of their diagnostic biopsy or curative-intent surgery and prior to any chemotherapy and/or radiation (participants may enroll on the first day of chemotherapy and/or radiation).

Institutions will identify a clinical research nurse (CRN) or clinical research associate that will be responsible for all aspects of this study. The designated CRN/CRA from each institution will be available to work with physicians during the clinical session to identify and recruit patients. The CRN/CRA or other members of the research team will discuss the details of this study with appropriate care and thoughtfulness as patients have recently received the diagnosis of a cancer. Because of the sensitive nature of a new diagnosis of cancer as well as financial questions, a script with talking points will be provided that address common concerns. Talking points will include: ensured privacy of financial information and sensitivity to new diagnosis. If the patient agrees, they will be screened for study eligibility at that time or at a subsequent visit as deemed appropriate by study personnel. This person will also be available to answer any questions regarding the study and obtain written informed consent.

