To evaluate the change of financial burden from baseline to the other time points (i.e., 3-month, 6-month, and 24month), the similar approaches described for the primary objective's assessment will be implemented. In addition, longitudinal data analysis will be conducted to estimate the measurements' trajectory across all five times points. Specially, linear (or generalized linear) mixed model will be fit to study the change in the mean response over time and also the effects of cancer type, stage, treatment plan and demographics, etc. on financial burden. In case the changes in the mean response over time are not linear, the quadratic trends or non-linear trends via spline may be considered in the modeling (61). Interactions will be evaluated as well. The above analyses may be repeated to explore the categorized COST measures (63, 64).

Logistic regressions will be fit to study whether or not the level of financial burden will impact the patient's adherence to clinical follow-up guidelines, which is defined as follows: "adherent" is defined as completing all of the follow up guidelines within the 24 month study period and includes an endoscopic evaluation of their colon or barium enema, routine history and physical at least twice, and serum carcinoembryonic (CEA) level checked at least twice. The details of adherence questions can be found in Section 9.2.4.1.

11.4.2.4 Evaluate the change of quality-of-life outcome (QoL) from baseline to 12 months and its association with predictors

FACT-G7, as described in Section 7.1.4, will be analyzed to evaluate the change of QoL from baseline to 12 months. The sum of the 7-item scores will be modeled as a continuous variable in the linear regressions (57). The predictors will include demographics (age, sex, marital status), clinical variables (stage of disease, malignancy type, chemotherapy status), and financial variables (COST score). Similar to the primary aim assessment, the impact of the baseline questionnaire variables (e.g., self-efficacy) and the system level variables (including being designated a minority/underserved site or not, availability of financial resources for patients) will be examined in the models as well. FACT-G7 at 6 months will be included as an adjustment covariate. Similar analysis will be conducted to evaluate the change of FACT-G7 from baseline to 24 months as well.

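### The 24-month form counts only visits to an undefined oncologist and has no rule for unknown answers, so recorded adherence may not match Section 11.4.2.3

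*Combined protocol and SAP*

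**What the plan says.** Section 9.2.4.1 states "We will define adherent versus non-adherent according to below questions and responses", and then "Considered ADHERENT if they answer the following (must have ALL) in bold". The outcome therefore has two categories and every component must qualify.

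- **Visit item:** "How many times has the patient been seen by their oncologist for a history/physical since ending treatment". Its unknown option reads "I don't know the reason", which does not fit a question about a count.
- **CEA item:** "How many times has the patient had a carcinoembryonic (CEA) serum checked since ending treatment". It names no clinician or centre and has an unknown option.
- **Endoscopy or barium enema item:** asked from the initial surgery onward, with no clinician or centre named and an unsure option.

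Section 11.4.2.3 defines adherence as completing all the guideline items within the 24-month study period: a bowel examination, plus "routine history and physical at least twice, and serum carcinoembryonic (CEA) level checked at least twice". It names no clinician and points back to 9.2.4.1 for the details of the questions. The outcome then enters logistic regressions on the level of financial burden. No covariates are listed for those models, although treatment plan is listed for the mixed model in the same section.

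On who enters the study, Section 6.3 says "Patients from a gastroenterology, surgical oncology, radiation oncology, or medical oncology clinic with newly diagnosed colon or rectal cancer are potential candidates". Section 4.1.8 admits patients who have surgery and choose no radiation or chemotherapy. Section 9.1 has the site research coordinator abstract the data from medical records.

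**The concern.** The form and the analysis section describe the visit component differently, and a patient can pass one and fail the other. Failing the visit item alone is enough to be scored non-adherent. The patients at risk are those whose follow-up examinations are all done by someone who is not an oncologist. These are plausibly mostly patients without chemotherapy.

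Treatment may in turn be related to the exposure. Section 1.2.6 hypothesises that patients receiving chemotherapy carry the higher burden, while saying this is not yet known. If so, the recording error would be related to burden.

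The unknown answers raise a separate problem. A coordinator who cannot find a record has learned nothing about whether care took place. If unknown is scored as non-adherent, and records are harder to find for patients under financial strain, an association can appear where none exists. Section 11.4.3 covers dropout and partly completed COST questionnaires and does not mention these answers.

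**Working it through.** The plan gives no adherence rate, odds ratio or power for this regression, so there is no figure of its own to reproduce. The check is a comparison of texts, followed by illustrations on assumed inputs.

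**1. The two definitions side by side**

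| Component | Form, 9.2.4.1 | Analysis, 11.4.2.3 |
|---|---|---|
| History and physical | Oncologist only, after treatment ended | At least twice, no clinician named, 24-month study period |
| CEA | Any source, after treatment ended | At least twice, 24-month study period |
| Bowel examination | Any source, after initial surgery | Once, 24-month study period |
| Unknown answer | Offered on every item | Not mentioned |

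The clinician restriction touches one component of three. The time windows differ on all three.

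**2. Who could be exposed**

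In Table 3 (Section 11.3.1), the strata unlikely to receive chemotherapy have thresholds of 180-190 (colon) and 36-38 (rectal). The chemotherapy strata have 180-190 and 144-152.

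- Share without chemotherapy: (180 + 36)/540 = 216/540 = 40%; upper thresholds (190 + 38)/570 = 228/570 = 40%.
- The note above the table gives rectal chemotherapy to no chemotherapy as about 1:4, the reverse of the thresholds. On that ratio the share is (180 + 144)/540 = 324/540 = 60%.

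This bounds who might lack a medical oncologist. It is not a misclassification rate, which the documents do not give.

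**3. Visit item, no true effect of burden**

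Assumed: true adherence 70% in everyone; high burden in 50% with chemotherapy and 30% without; 40% without chemotherapy; a fraction m of adherent no-chemotherapy patients seen only outside oncology.

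- Recorded adherence without chemotherapy: a = 0.7(1 - m).
- High burden: (0.30 x 0.7 + 0.12a)/0.42. Low burden: (0.30 x 0.7 + 0.28a)/0.58. The weights are 0.6 x 0.5 = 0.30, 0.4 x 0.3 = 0.12, 0.6 x 0.5 = 0.30 and 0.4 x 0.7 = 0.28.

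| m | a | High burden | Low burden | Odds ratio |
|---|---|---|---|---|
| 10% | 0.63 | 0.680 | 0.666 | 1.06 |
| 30% | 0.49 | 0.640 | 0.599 | 1.19 |
| 50% | 0.35 | 0.600 | 0.531 | 1.32 |

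Within chemotherapy patients recorded adherence is 0.70 in both burden groups; without chemotherapy it is a in both. The chemotherapy-adjusted odds ratio is therefore 1.0.

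**4. Unknown answers, no true effect of burden**

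Assumed: true adherence 70%; records unknown for 10% of high-burden and 3% of low-burden patients, regardless of true adherence.

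- Scored non-adherent: 0.7 x 0.90 = 0.63 and 0.7 x 0.97 = 0.679; odds ratio (0.63/0.37)/(0.679/0.321) = 0.80.
- Set to missing: 0.63/0.90 = 0.70 and 0.679/0.97 = 0.70; odds ratio 1.0.

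**5. General behaviour**

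Let f be the fraction of truly adherent patients recorded as non-adherent, with true adherence of 60% or 75% in the low-burden group.

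- Equal f = 20% in both groups, true odds ratio 0.50: observed 0.57-0.62. With 197 per burden group (394/2, assuming the 394 of Section 11.3.2 split equally), power falls from 0.89-0.93 to 0.67-0.79. With no true effect, equal f leaves the odds ratio at 1.00.
- Unequal f (20% against 10%), no true effect: 1.27-1.39 if the low-burden group loses more, 0.72-0.79 if the high-burden group does.

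**The case against.** The strongest reply is that there is no conflict: 11.4.2.3 sends the reader to 9.2.4.1, which is the operational definition, and silence about the clinician is not a contrary rule. It stands that 11.4.2.3 does not say any clinician will do. But the two texts still yield different outcomes for the same patient, and the cross-reference does not say which governs.

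A reader might infer that everyone followed by a surgeon, a gastroenterologist or another centre is misclassified. The documents do not support that. Surgical oncology is among the recruiting clinics, so a surgical oncologist may count. The visit item has no site restriction, so an oncologist elsewhere counts. Having no chemotherapy is not the same as having no oncologist.

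A reader might also infer that unknown answers are scored non-adherent. That is the literal reading of a two-category rule requiring every qualifying answer, but it is nowhere stated. The bold type marking those answers is not visible in the text copy of the protocol, and the general missing-data language of 11.4.3 does not rule out treating unknowns as missing.

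Finally, every rate in the illustrations is assumed, and the 1.19 disappears with one covariate that the plan does not exclude. That stands too. Adjustment cannot, however, recover visits the form never recorded, so a true effect would still be attenuated.

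**Conclusion.** The point holds as a mismatch between form and analysis plan, together with a missing rule for unknown answers. Some patients may be recorded as non-adherent although they meet the 11.4.2.3 wording. How many is unknown, and so are the size and direction of any bias. Error unrelated to burden attenuates a true effect; error related to burden can move the estimate either way.

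The figures of 1.06-1.32 (unadjusted, 1.0 after chemotherapy adjustment) and 0.80 show what is possible on assumed inputs. They do not estimate what will happen in this study. The reach is limited to the adherence part of secondary endpoint 2.2.3; the primary COST comparison is unaffected. The change is still worth making because it is cheap, and visits not captured on the form could be recovered only by re-abstraction.

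**What to change.** 1. Reconcile the visit item in 9.2.4.1 with 11.4.2.3. Either have the form capture follow-up histories and physicals regardless of clinician type, or have it record the clinician type, and state which visits count. That choice is the sponsor's.
2. Align the time window, since the form counts from the end of treatment or from surgery and 11.4.2.3 uses the 24-month study period. Correct the unknown option on the visit item.
3. State that adherence is missing when any component is unknown and no other component has failed. Add one sensitivity run scoring unknowns as non-adherent.
4. Include the chemotherapy stratum, already collected, as a covariate in the adherence model.

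The cost is a revised form item and a few sentences in the analysis plan. The downside is a few more missing adherence outcomes and a re-check of any 24-month forms already submitted.

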1.2.6 Description of the Patient Population and Assessment Time Points in Proposed Study

This study will focus on patients receiving curative-intent treatment for colon or rectal cancer specifically for several reasons. Colon and rectal cancer were chosen because these are common malignancies that are most frequently diagnosed in the curative-intent setting (45). Because these patients typically have longer survival than those with metastatic disease, they potentially have a longer period of time to be impacted by the costs of their cancer and changes in employment. Previous studies have largely focused only on patients receiving chemotherapy and/or with metastatic disease (18, 42, 46). The recently opened SWOG trial investigating financial burden (PI: [name]) focuses on metastatic disease, and our proposed study of early stage disease will synergize with her work and will contain some common variables to allow for cross-study analysis.

There remain many unanswered questions about the financial burden that our study will address. We hypothesize that those who receive chemotherapy may have higher burden than those who do not, however this is currently unknown and will be prospectively studied in this study. We will stratify by both disease type and receipt of chemotherapy to allow for robust comparisons between these groups, which has not been previously reported in a prospective study. These comparisons may be important as we develop implementation studies and education to focus on malignancy types and treatment settings that demonstrate the highest level of burden.

We chose the time points, baseline at diagnosis, 3, 6, 12, and 24 months because they correlate with important landmarks in the treatment of colorectal cancer. At three months after diagnosis, most patients are in the initial phase of their therapy (either surgery for colon cancer or chemo-radiation for rectal). By 6 months, most patients are approaching the end of their planned therapy, and by 12 months most patients are typically done with therapy. The 24 month time point is an opportunity to collect data related to adherence to follow-up guidelines, more specifically either a colonoscopy, sigmoidoscopy, or barium enema. By analyzing data at each of these time points, there is hope to gain better understanding of the timing of changes in employment and financial burden to inform when in the cancer continuum would a future intervention be optimal.

2. Objectives

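### Adherence needs two visits and two CEA tests counted from the end of treatment to month 24, so longer-treated patients have less time to qualify, and the adherence regression names no treatment term

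*Combined protocol and SAP*

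**What the plan says.** Section 9.2.4.1 builds adherence from three items, all of which must be met. Two are counts that start when treatment ends: "How many times has the patient been seen by their oncologist for a history/physical since ending treatment" and "How many times has the patient had a carcinoembryonic (CEA) serum checked since ending treatment". The highest answer to each is a single category for anything above two. The endoscopy or barium enema item runs from initial surgery, although the lead-in to that section speaks of completion of therapy.

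The reading time is fixed. Section 9.2.4 says of the 24-month form: "This form is completed once the participant has completed 24 months of study".

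Section 11.4.2.3 sets one threshold for all patients, "routine history and physical at least twice, and serum carcinoembryonic (CEA) level checked at least twice", plus a colon examination, but describes the window as "completing all of the follow up guidelines within the 24 month study period". On the analysis it says: "Logistic regressions will be fit to study whether or not the level of financial burden will impact the patient's adherence". It names no covariate for this model and no allowance for time since treatment ended. By contrast, the mixed model in the same section names cancer type, stage, treatment plan and demographics, and the FACT-G7 model in 11.4.2.4 names chemotherapy status.

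Section 1.2.6 hypothesises that "those who receive chemotherapy may have higher burden than those who do not" and adds that this is not yet known. It also says that most patients are near the end of planned therapy at 6 months and finished by 12. Section 4.1.8 admits patients who have surgery alone.

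**The concern.** A fixed count over windows of unequal length is easier to reach in the longer window, even when two patients attend equally often. Treatment length sets the window. If treatment is also related to financial burden, it is a common cause of the predictor and the outcome, and a model without a treatment term attributes part of the window effect to burden.

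Adherence at 24 months is part of secondary endpoint 2.2.3, and Section 1.2.6 gives it as the reason for the 24-month assessment. A false link between burden and missed follow-up, or a true link masked, would feed into the interventions that the study is meant to inform.

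A separate matter needs no assumption. The analysis plan describes a count over the study period, and the form collects a count after treatment. For a patient treated for 6 to 12 months these can differ, and the study-period count cannot be recovered from the answers.

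**Working it through.** **Plan's own figures.** The documents give no size or power for the adherence analysis, so I use the 12-month completer number from Section 11.3.2. It reproduces: SD of change = 12 × √(2 × (1 − 0.2)) = 15.18, and n = (15.18 × (1.960 + 1.282) / 2.5)² ≈ 388 by the paired normal formula, against the stated 394. Simulated signed-rank power at 394 is 0.888 against 0.90. 394 / 0.70 = 563. No 24-month attrition is stated, so n = 394 is itself an assumption here.

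**Counting windows.**
- Therapy ending at 6 to 12 months (1.2.6) leaves 24 − 12 = 12 to 24 − 6 = 18 months.
- Surgery alone near baseline leaves about 22 to 24 months. This assumes that treatment ends at surgery.
- These are approximate, because registration may follow diagnosis by up to 60 days.

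**Chance of qualifying with the same behaviour in both groups.** Assume visits and CEA tests are independent Poisson counts with mean m = window / mean interval. Then P(at least 2) = 1 − e^(−m)(1 + m), squared for both. At a 6-month mean interval:
- 24 months, m = 4: 0.908, squared 0.83
- 18 months, m = 3: 0.801, squared 0.64
- 12 months, m = 2: 0.594, squared 0.35

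If CEA is always drawn at the visit, the unsquared figures apply. At a 3-month mean interval the squared values are 0.99, 0.97 and 0.83; at 12 months they are 0.35, 0.20 and 0.07.

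With strictly regular 6-monthly visits, a 12-month window holds 12 / 6 = 2 visits, so the shorter window costs nothing; 3-monthly visits give 4. With regular 12-monthly visits, 24 months gives 2 but 12 or 18 months gives 1.

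**Effect on the regression when burden has no effect.** Inputs:
- COST mean 25, SD 12 (11.3.2).
- Chemotherapy share (180 + 144) / (180 + 180 + 36 + 144) = 324 / 540 = 60%, from the Table 3 thresholds. The note in 11.3.1 gives the rectal ratio the other way round, which would make it 216 / 540 = 40%.
- 24 months for untreated patients.
- COST gap by chemotherapy of 0, 2.5 or 5 points (assumed; the documents give none).

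Odds ratios of adherence are per 10 points worse COST. False-positive rates are two-sided 5% tests at n = 394 over 1,000 replicates, with a 6-month mean interval:

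| COST gap | Treated window | OR, no chemotherapy term | False positives | OR, with term | False positives |
|---|---|---|---|---|---|
| 0 | 18 | 1.00 | 6.5% | 1.00 | 6.4% |
| 0 | 12 | 1.00 | 5.1% | 1.00 | 5.1% |
| 2.5 | 18 | 0.97 | 6.5% | 1.00 | 4.6% |
| 2.5 | 12 | 0.93 | 13% | 1.00 | 4.2% |
| 5 | 18 | 0.93 | 12% | 1.00 | 4.2% |
| 5 | 12 | 0.86 | 46% | 1.01 | 6.2% |

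**Closer to the actual outcome.** The table leaves out endoscopy. With CEA drawn at the visit, endoscopy done in 70% (assumed) and 23 months for untreated patients, the 5-point odds ratios move to about 1 / 1.02 = 0.98 (18-month window) and 1 / 1.07 = 0.93 (12-month window). A re-run confirmed both.

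**Direction.** If treated patients are seen at random every 6 months over 18 months and untreated patients every 12 months over 24, both probabilities change: 0.64 of treated patients qualify against 0.35 of untreated. With a 5-point gap the null odds ratio is then 1.09. At 6 against 8 months the mean counts are equal (18 / 6 = 24 / 8 = 3) and it is 1.00.

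**The case against.** A reader might infer that the regression is biased, and biased towards showing that burden harms adherence. The documents do not support that. Three conditions must hold together: burden differs by chemotherapy, the fitted model omits treatment, and visits are sparse or irregular enough for the window to matter. The first is only hypothesised, and a 5-point gap is twice the 2.5-point change that Section 11.3.2 assumes for the whole cohort. On the second, the plan is silent rather than exclusionary: Section 7.1.7 lists sociodemographics, insurance and self-efficacy as predictors for all objectives, and chemotherapy is a declared stratification factor. On the third, regular 3- or 6-monthly follow-up removes the effect. The sign can also reverse. Nor does 11.4.2.3 say which COST time point enters the model. Baseline COST is meant to precede chemotherapy or coincide with its start, when a gap caused by treatment costs should be small.

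The window mismatch also has a charitable reading. Section 11.4.2.3 refers to 9.2.4.1 for detail, and surveillance after treatment that is completed by month 24 satisfies both texts.

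All of this limits size and direction. What remains is that the windows are unequal by design, that no section puts chemotherapy or time off treatment in this model although neighbouring models have such terms, and that the two sections describe the count differently.

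**Conclusion.** The point holds as a risk of confounding by unequal observation time in one secondary regression, together with a mismatch between two descriptions of the same outcome. The unequal windows and the mismatch come from the documents, apart from the assumption that surgery-only treatment ends near baseline.

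The size is conditional. It is nil if burden does not differ by chemotherapy or if visits are regular at 3 or 6 months. It is a null odds ratio of about 0.86 to 0.93 per 10 points worse COST with random 6-monthly contact and an assumed 5-point gap, and nearer 0.93 to 0.98 under the coincident-CEA and endoscopy assumptions above. It exceeds 1 if untreated patients see an oncologist much less often. Under every scenario in the table, a chemotherapy term brings the null odds ratio back to about 1.00. The primary endpoint and the sample size are untouched.

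**What to change.** 1. In Section 11.4.2.3, prespecify chemotherapy stratum as a covariate in the adherence logistic model. It is already collected.
2. Add time since end of treatment as far as the data allow. Section 9.2.3 records treatment status at 3, 6, 12 and 24 months, which places the end of treatment within an interval. An end-of-treatment date would need an added field on the clinical form.
3. Reconcile Sections 9.2.4.1 and 11.4.2.3 on one counting window, including the starting point of the endoscopy item, so that the outcome can be derived from what the form collects.

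Scoring visits and CEA tests as a rate per month off treatment is not a workable alternative, because the form does not distinguish counts above two.

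The cost is a few lines of analysis-plan text, one or two degrees of freedom, and possibly one form field. Fixing the covariates now also avoids choosing the model after the results are known.
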